14.5 Physical Examination

Physical examination is performed at Baseline, Week 28, and Week 52(EOT/ET). Physical examination results (normal, abnormal, and not done) will be summarized at each visit in a frequency table by body system.

14.6 Other Safety Variables

14.6.1 Suicidality Based on C-SSRS

The event counts and the number and percentage of subjects reporting any post double-blind Baseline suicidal ideation, suicidal behavior, or suicidality will be tabulated by the double-blind treatment group in the antecedent studies across the timepoints of both the antecedent study and the open-label Study ACP-103-055. The event counts and the number and percentage of subjects reporting any post-Baseline non-suicidal self-injurious behavior will also be tabulated. For calculating the percentages, the denominator will be the number of subjects in the Safety Analysis Set. In addition, a summary counting of any reports post open-label Baseline will be presented.

14.6.2 CGI-S Score Based on ESRS-A

Descriptive statistics for ESRS-A CGI-S score will be tabulated by the double-blind treatment group in the antecedent studies at scheduled timepoints. The summaries of the change from Baseline results will be presented in two ways (main analysis and exploratory analysis) as specified in [Section 5.1](#).

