### **6.3.6 Extrapyramidal Symptom Rating Scale–Abbreviated**

The ESRS ([Chouinard and Margolese 2005](#)) was developed to assess drug induced movement disorders such as parkinsonism, akathisia, dystonia and tardive dyskinesia with established reliability, validity, and sensitivity. It consists of a questionnaire of parkinsonian symptoms, physician examination of parkinsonism, dyskinetic movements, and global impression of tardive dyskinesia. The ESRS-A, an accepted modified form of the original ESRS, will be used during the study to monitor for any worsening in extrapyramidal symptoms or signs at all scheduled and unscheduled visits.

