## **9.5.2 Exploratory Analyses**

For the C-SSRS, the number and percentage of subjects with suicidal ideation or suicidal behavior during this study will be tabulated.

Descriptive summary statistics for ESRS-A observed values and change from Baseline will be provided by timepoint.

Number and percentage of subjects with sexual dysfunction (a total score of  $\leq 47$  for men and  $\leq 41$  for women) will be summarized and shift tables will be presented.

Vital sign measurements and body weight, including changes from Baseline, will be summarized by timepoint using descriptive statistics. The number and percentage of subjects with changes from Baseline (increases and decreases separately) in body weight of  $\geq 7\%$  will also be provided by timepoint.

Clinical laboratory parameters, including changes from Baseline, will be summarized by timepoint using descriptive statistics. For selected parameters, the number and percentage of subjects with potentially clinically important post-baseline laboratory values will be summarized by timepoint as well as across all post-baseline timepoints. The criteria for potentially important values will be specified in the SAP.

Descriptive summary statistics for HAMD-17, CGI-S, SDS, CSFQ-14, and KSS observed values, and change from Baseline will be provided by timepoint.

Treatment responder rate and treatment remission rate will be summarized by timepoint.

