5.1 General Data Reporting Conventions

For continuous variables, the following summary statistics will be provided: number of subjects, mean, standard error of the mean (SE), standard deviation (SD), minimum, maximum, and median. Unless specified otherwise, means, and medians will be presented to one more decimal place than the raw data, and the SDs and SEs will be presented to 2 more decimal places than the raw data.

For categorical variables, summaries will include the number and percentage of subjects in each category, using the number of subjects with non-missing values as the denominator for the percentages (unless otherwise specified). Categories with zero counts will not have zero percentages displayed. Percentages will be presented to 1 decimal place.

When converting number of days to months, it will be calculated as the number of days divided by 365.25 and then multiplied by 12. When converting number of days to years, it will be calculated as the number of days divided by 365.25.

No hypothesis testing is planned. Descriptive summaries of all safety and efficacy endpoints will be provided.

All safety and efficacy endpoints will be summarized for the Safety Analysis Set. In addition, summaries by treatment group according to the original double-blinded treatment actually received in the antecedent study (placebo or pimavanserin) will also be provided.

For each continuous measure in safety and efficacy analyses, change from Baseline results will be presented in two ways:

1. Main analysis: using the Baseline from Study ACP-103-055 and reporting the changes across Study ACP-103-055 timepoints
2. Exploratory analysis: using the Baseline from the antecedent study (ACP-103-054 or ACP-103-059), and reporting the changes across Study ACP-103-055 timepoints

For the treatment responder rate, the summary will also be presented in two ways:

1. Main analysis: using the Baseline from Study ACP-103-055 and reporting the rate across Study ACP-103-055 timepoints
2. Exploratory analysis: using the Baseline from the antecedent study (ACP-103-054 or ACP-103-059), and reporting the rate across Study ACP-103-055 timepoints

The treatment remission rate and the percentage of subjects with sexual dysfunction will also be summarized across Study ACP-103-055 timepoints using the Baseline from Study ACP-103-055 and the Baseline from the antecedent double-blind studies as reference points.

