5.2.2 Extrapyramidal Symptom Rating Scale–Abbreviated (ESRS-A)

The ESRS-A is assessed at Baseline, Weeks 2, 4, 8, 12, 16, 28, 40, and 52 (EOT/ET). The ESRS was developed to assess drug induced movement disorders such as parkinsonism, akathisia, dystonia and tardive dyskinesia with established reliability, validity, and sensitivity. The ESRS-A, an accepted modified form of the original ESRS, is used during the study to monitor for any worsening in extrapyramidal symptoms or signs at scheduled and

unscheduled visits. The CGI-S for each movement subtype (i.e., parkinsonism, dystonia, dyskinesia, and akathisia) rates the severity of a subject's movement disorder and the CGI-S score for each movement subtype ranges from 0 to 5:

0 = Absent	1 = Minimal	2 = Mild
3 = Moderate	4 = Severe	5 = Extreme

Higher CGI-S scores denote more severe movement disorder. Missing scores will not be imputed.

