5.3.1 Unscheduled Assessments

Both scheduled and unscheduled assessments, including early termination visits and remote visits, will be considered for planned timepoint summaries. All assessments will be presented in data listings.

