5.3.2 Multiple Measurements within Visit Windows

If more than one assessment falls within a given window then the assessment closest to the target study day will be selected for the by-visit summaries. If two assessments are equidistant from the target day then the chronologically last assessment will be used for summary. Exceptions may be made for incomplete assessments, in which case, more complete assessments may be given priority. Details are provided in a separate programming conventions document.

For safety summaries where the most extreme values should be selected, e.g. overall post-baseline minimum, overall post-baseline maximum, and potentially clinically important values for overall post-Baseline summaries, all non-missing post-Baseline values should be considered, regardless of whether the value is selected for the by-visit summaries. All results will be presented in data listings.

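### The planned ESRS-A tables do not show how many subjects' extrapyramidal scores worsened, and an unscheduled score drops out when another in its window is closer to target

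*SAP*

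**What the plan says.** Extrapyramidal symptoms are a named exploratory safety objective (Protocol 2.2, SAP 2.2). Protocol 6.3.6 says the ESRS-A is used "to monitor for any worsening in extrapyramidal symptoms or signs at all scheduled and unscheduled visits", and Protocol 6.5 lists it among the assessments for an unscheduled visit.

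For analysis, Protocol 9.5.2 states: "Descriptive summary statistics for ESRS-A observed values and change from Baseline will be provided by timepoint". SAP 14.6.2 carries this out: "Descriptive statistics for ESRS-A CGI-S score will be tabulated by the double-blind treatment group in the antecedent studies at scheduled timepoints". It adds that change from Baseline is shown against both the open-label and the antecedent-study Baseline.

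Three general rules in the SAP determine what reaches the table:

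- **Statistics and precision (5.1).** Continuous variables are reported as "number of subjects, mean, standard error of the mean (SE), standard deviation (SD), minimum, maximum, and median". By default, "means, and medians will be presented to one more decimal place than the raw data". SAP 5.2.2 says the "CGI-S score for each movement subtype ranges from 0 to 5", in whole numbers, so means print to one decimal.
- **Eligibility (5.3.1).** "Both scheduled and unscheduled assessments, including early termination visits and remote visits, will be considered for planned timepoint summaries".
- **Selection (5.3.2).** "If more than one assessment falls within a given window then the assessment closest to the target study day will be selected". Ties go to the later assessment, and a more complete assessment may take priority over an incomplete one. A separate rule brings in every post-Baseline value, but only for summaries that pick out extremes. SAP 14.6.2 specifies no such summary.

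**The concern.** An instrument used to watch for any worsening raises a subject-level question: how many subjects got worse, and how far? By-visit descriptive statistics do not answer it. An average over the whole group dilutes a few large changes, and a maximum shows one value at one visit.

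The selection rule adds to this. A visit prompted by new symptoms need not fall near a target day. If a scheduled assessment in the same window is closer to target, the unscheduled score stays out of the by-visit table, and no worst-value summary picks it up.

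Other safety measures are treated differently. Laboratory values and vital signs have counts of subjects with potentially clinically important values over all post-Baseline data, unscheduled and out-of-window values included (SAP 14.2, 14.3). ECG has overall post-Baseline counts and a worst interpretation (14.4). The C-SSRS counts subjects with any post-Baseline report, unscheduled visits included (5.2.1, 14.6.1). Sexual dysfunction is reported as number and percentage (14.6.3). No reason is given for leaving the ESRS-A without an equivalent. At stake is whether the study report can say how many subjects had a worsened ESRS-A score.

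**Working it through.** The documents give no figure on this point to reproduce. Two direct checks follow.

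**(a) When does an unscheduled score reach the table?**

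Inputs: windows and targets from SAP Table 1; visit windows from Protocol Table S-1; the closest-to-target rule with ties to the later assessment from SAP 5.3.2. First dose is the day after Baseline (Protocol 5.1.3), so a visit exactly w weeks after Baseline falls on study day 7w, one day before the target of 7w + 1. Assume one scheduled and one unscheduled ESRS-A in the window, on different days.

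- *Scheduled visit at its nominal date (target − 1).* The unscheduled score wins only on the target day or the day after (a tie, later wins): 2 days per window.
- *Scheduled visit as far from target as its visit window allows.* Weeks 2 to 12: target − 4, so 7 closer days plus 1 later tie = 8. Weeks 16 to 40: target − 8, so 15 + 1 = 16. Week 52: target + 6, so 11 closer days, and the tie is earlier and loses = 11.

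| Window | Study days | Other days available | Wins, nominal | Wins, farthest |
|---|---|---|---|---|
| Week 2 | 2–21 | 19 | 2 | 8 |
| Week 4 | 22–42 | 20 | 2 | 8 |
| Week 8 | 43–70 | 27 | 2 | 8 |
| Week 12 | 71–98 | 27 | 2 | 8 |
| Week 16 | 99–154 | 55 | 2 | 16 |
| Week 28 | 155–238 | 83 | 2 | 16 |
| Week 40 | 239–322 | 83 | 2 | 16 |
| Week 52 | 323–379 | 56 | 2 | 11 |
| Total | | 370 | 16 | 91 |

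Left out: 370 − 16 = 354 days (354/370 = 96%) with nominal visits, and 370 − 91 = 279 days (279/370 = 75%) with visits farthest from target. Example: a score on day 140 is 27 days from the Week 16 target of 113, and loses to a scheduled visit on day 112, 1 day from it. With no other assessment in the window, the day 140 score is used.

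These are shares of calendar days, not probabilities. The documents give no frequency or timing of unscheduled visits.

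**(b) How many subjects can worsen while the mean change prints as 0.0?**

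If k of N subjects worsen by d points and all others are unchanged, the mean change is k × d / N. It prints as 0.0 while k × d / N < 0.05. The largest such k:

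| N | d = 1 | d = 3 | d = 5 |
|---|---|---|---|
| 420 (planned) | 20 (20/420 = 0.048) | 6 (18/420 = 0.043) | 4 (20/420 = 0.048) |
| 200 (assumed) | 9 (9/200 = 0.045) | 3 (9/200 = 0.045) | 1 (5/200 = 0.025) |
| 100 (assumed) | 4 (4/100 = 0.04) | 1 (3/100 = 0.03) | 0 |

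SAP 3.5 says the actual number will be below the original estimate but gives no figure, hence the assumed rows.

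In the N = 420, d = 3 case, the printed mean change is 0.0 and the maximum is 3 whether 1 subject or 6 worsened. The SD does move: with SD = d × √[k(N − k) / (N(N − 1))], it is 3 × √[419/(420 × 419)] = 0.15 for k = 1 and 3 × √[(6 × 414)/(420 × 419)] = 0.36 for k = 6. It yields a count only if the pattern of changes is already known.

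**The case against.** The other side has good points, and several narrow the concern.

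- **The table is not means alone.** A reader might infer that moderate or severe worsening could vanish from it. The documents do not support that for selected scores: a selected change from 0 to 3 prints as a maximum change of 3. If 2% of subjects made that change, the mean would be 0.02 × 3 = 0.06, which prints as 0.1. What is missing is the number of subjects.
- **Unscheduled scores are not excluded as a class.** A reader might infer exclusion from the reference to scheduled timepoints, or conclude that such scores are usually discarded. SAP 5.3.1 makes them eligible, and nothing in the documents says how often or when they arise. A symptom that persists to the next selected assessment is still captured, and a subject who stops early should have an early termination visit that includes the ESRS-A (Protocol 4.4.1, Table S-1).
- **Other outputs exist.** All data are listed (SAP 5), and movement symptoms reported as adverse events enter the TEAE tables with subject counts and maximum severity (SAP 14.1). These help, but a listing is not a summary and the TEAE tables count only what was reported as an event. The explicit instruction to update the adverse event page for new or worsening symptoms stands in Protocol 6.3.8.5, for visits where the motor examination cannot be done; Protocol 6.3.6 has no such instruction.
- **The SAP follows the protocol.** It does. Protocol 9.5.2 asks for by-timepoint descriptive statistics, so the two documents do not contradict each other. The issue is an analysis too thin for its purpose.
- **Table specifications are in a separate document (SAP 1).** A further ESRS-A table could appear there, but the SAP does not require one.
- **Any threshold would be chosen from outside the documents.** This is fair. Neither document defines an important ESRS-A change, so the fix should lead with a summary that needs no cut-off.

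**Conclusion.** The point holds as a gap in an exploratory, descriptive safety analysis. No ESRS-A table in the SAP gives the number of subjects whose score worsened, and an unscheduled score stays out of the tables whenever another assessment in its window is closer to target. The size is illustrated by the 20 (1 point) or 6 (3 points) of 420 subjects who could worsen behind a printed mean change of 0.0. Those counts assume that everyone else is unchanged and that the default one-decimal display applies. The shares of days in check (a) show how the selection rule works; they do not estimate how many scores would be lost. The gap does not mean that extrapyramidal safety goes unreported, because the maximum, the listings and the TEAE tables each cover part of it.

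**What to change.** Add to SAP 14.6.2, for each movement subtype (parkinsonism, dystonia, dyskinesia, akathisia), overall and by antecedent treatment group:

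1. a shift table from open-label Baseline score to worst post-Baseline score;
2. the number and percentage of subjects with any post-Baseline increase over open-label Baseline.

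Use all post-Baseline assessments, including unscheduled and out-of-window ones, and state that the all-values rule in SAP 5.3.2 applies. The denominator is subjects with a Baseline and at least one post-Baseline score, as SAP 14.2 already does for laboratory shifts to the overall minimum or maximum. A count of subjects with a post-Baseline score of 3 or more is optional: 3 is labelled Moderate in SAP 5.2.2, but the documents do not set it as a threshold.

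The cost is one extra descriptive table from data already collected. No planned table changes and no new data are needed. With a reduced sample, many shift cells may be empty.

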14.6.3 Sexual Dysfunction Based on CSFQ-14

The number and percentage of subjects with sexual dysfunction defined as a CSFQ-14 total score of ≤ 47 for men and ≤ 41 for women will be tabulated by the double-blind treatment group in the antecedent studies across the antecedent study double-blind baseline visit and the open-label Study ACP-103-055 timepoints. For calculating the percentages, the denominator will be the number of subjects in the Safety Analysis Set.

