3.6 Coronavirus Disease 2019

In March, 2020, the emerging coronavirus disease 2019 (COVID-19) pandemic resulted in implementation of urgent safety measures designed to ensure subject safety. Mechanisms to record information on the potential impact of the COVID-19 pandemic on data itself, as well as data collection and integrity, were implemented (as detailed in the “Guidance for Site Documentation and Data Management Querying of Data Impacted by COVID-19” [GSD] in the Data Management Plan).

Screening and enrollment into studies ACP-103-054 and ACP-103-059 were closed and enrollment into ACP-103-055 was allowed to continue. The impact of COVID-19 on the statistical analysis is discussed in each of the relevant sections of this SAP.

Subjects who remained in this study who could not attend clinic visits were allowed to participate in remote visits via telephone or video, or site staff conducted the visit in a subject’s home. Sites were required to document details of all visits that are administered remotely.

Afterwards, ACP-103-055 was stopped early and the remaining subjects were discontinued in the study.

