5.2.3 Changes in Sexual Functioning Questionnaire Short Form (CSFQ-14)

The CSFQ-14 is assessed at Baseline, Weeks 2, 4, 8, 12, 16, 28, 40, and 52 (EOT/ET). The CSFQ-14 is a 14-item version of the CSFQ. This is a patient-facing questionnaire, with a male version and a female version. The total score ranging from 14 to 70 will be calculated as the sum of the scores for all 14 items. Higher total scores denote better sexual functioning. Missing item scores will be imputed using the arithmetic mean of the non-missing item scores and rounded to the nearest integer. The total score will be considered as missing if there are missing scores for 3 or more items.

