Number and percentage of subjects with potentially clinically important (PCI) laboratory values at scheduled post-Baseline visits and overall post-Baseline will be summarized by Baseline status (all or within normal range) for selected parameters. PCI criteria are listed in [Table 2](#) and [Table 3](#). For the overall post-Baseline summaries, all post-Baseline values will be considered, including unscheduled and out of window values. Subjects with multiple PCI values for a given parameter will be counted only once for that parameter. For the by-visit summary, the numerator for the percentage is the number of subjects with a post-Baseline PCI value for the given parameter and visit, and the denominator is the number of subjects with non-missing values for the given parameter and visit. For the overall post-Baseline summary, the numerator for the percentage is the number of subjects with at least 1 post-Baseline PCI value for the given parameter, and the denominator is the number of subjects with at least 1 post-Baseline value for the given parameter. For hemoglobin, hematocrit, and uric acid, the count and percentage of subjects with PCI values will be presented for each gender as well as for both genders combined. A listing of all PCI values in study ACP-103-055 will be provided. This listing will include all observations from study ACP-103-055 for those subjects and parameters for which at least one PCI value (including OL Baseline) was observed.

Table 2 Criteria for Potentially Clinically Important Laboratory Values – Hematology and Chemistry

Analyte	Conventional Unit	Low PCI Criteria	High PCI Criteria	SI Unit	Low PCI Criteria	High PCI Criteria
Hematology (whole blood)						
Hemoglobin (male)	g/dL	<11	>18	g/L	<110	>180
Hemoglobin (female)	g/dL	<10	>17	g/L	<100	>170
Hematocrit (male)	%	<30	>55	L/L	<0.3	>0.55
Hematocrit (female)	%	<30	>50	L/L	<0.3	>0.5
Leukocyte (White Blood Cell Count)	x 10 ³ /uL	≤2.8	≥15	x 10 ⁹ /L	≤2.8	≥15
Neutrophils	x 10 ³ /uL	≤1.5	No upper limit	x 10 ⁹ /L	≤1.5	No upper limit
Platelet Count	x 10 ³ /uL	≤75	≥700	10 ⁹ /L	≤75	≥700
Chemistry (serum or plasma)						
ALT (SGPT)	U/L	No lower limit	≥3 X ULN	U/L	No lower limit	≥3 X ULN
AST (SGOT)	U/L	No lower limit	≥3 X ULN	U/L	No lower limit	≥3 X ULN
Total Bilirubin	mg/dL	No lower limit	≥1.5 ULN	umol/L	No lower limit	≥1.5 ULN
BUN	mg/dL	No lower limit	≥30.0	mmol/L	No lower limit	≥10.71
Creatine Kinase (CK)	U/L	No lower limit	≥3 ULN	U/L	No lower limit	≥3 ULN

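### SAP 14.6.3 divides by-visit sexual-dysfunction counts by the whole Safety Analysis Set, so missing CSFQ-14 scores lower the reported percentage

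*SAP*

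**What the plan says.** SAP 14.6.3 defines sexual dysfunction as a CSFQ-14 total at or below 47 in men and 41 in women. It tabulates the number and percentage by prior double-blind treatment at the antecedent study's baseline visit and the "open-label Study ACP-103-055 timepoints. For calculating the percentages, the denominator will be the number of subjects in the Safety Analysis Set".

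Other parts of the SAP bear on this rule:

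- **General rule.** SAP 5.1 summarises categorical variables "using the number of subjects with non-missing values as the denominator for the percentages (unless otherwise specified"). Section 14.6.3 is thus an explicit override.
- **By-visit reading.** SAP 5.1 also states: "The treatment remission rate and the percentage of subjects with sexual dysfunction will also be summarized across Study ACP-103-055 timepoints". Remission has no denominator of its own elsewhere in the SAP, so it keeps the non-missing default.
- **When a total is missing.** SAP 5.2.3 imputes one or two missing items, but "The total score will be considered as missing if there are missing scores for 3 or more items". SAP 12.3 does not impute totals that are still missing.
- **Which assessments count.** SAP 5.3.1: "Both scheduled and unscheduled assessments, including early termination visits and remote visits, will be considered for planned timepoint summaries". Each is placed by its study day, and Table 1 in SAP 5.3 gives Week 52 as Days 323 to 379.
- **Other by-visit safety percentages.** For potentially clinically important laboratory values, SAP 14.2 says "the denominator is the number of subjects with non-missing values for the given parameter and visit". Sections 14.3 (vital signs) and 14.4 (ECG) use the same rule.
- **Early stop.** SAP 3.6: "Afterwards, ACP-103-055 was stopped early and the remaining subjects were discontinued in the study".

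**The concern.** Membership of the Safety Analysis Set requires one open-label dose, not a CSFQ-14 score (SAP 4). A subject with no assessment in a visit window, or with three or more items missing, therefore adds to the denominator and never to the numerator. For a harm, that is the optimistic assumption: no data is read as no dysfunction.

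Sexual dysfunction is a listed exploratory safety endpoint (Protocol 2.2.1; SAP 14). If prevalence among scored subjects stays constant, the printed percentage falls as subjects leave. A reader following the row from baseline to Week 52 could take attrition for recovery. The table is also split by prior treatment, so if the two groups differ in completeness, a difference appears that has nothing to do with sexual function.

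The same denominator sentence stands in SAP 14.6.1, where it does less harm. There it applies to cumulative counts of subjects "reporting any post double-blind Baseline suicidal ideation, suicidal behavior, or suicidality", not to a state measured at each visit.

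**Working it through.** The plan states no figure to reproduce, so the check is an identity with illustrations.

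**Inputs.** For one visit and one prior-treatment group:
- N = subjects in the Safety Analysis Set (denominator in SAP 14.6.3)
- s = subjects with a CSFQ-14 total at that visit (SAP 5.2.3, 5.3 and 12.3)
- d = scored subjects at or below the cut-off (numerator in SAP 14.6.3)

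**Identity.** Reported share: d/N = (d/s) × (s/N). Write p = d/s for prevalence among scored subjects and r = s/N for the share scored. Then:
- reported = p × r, which can never exceed r
- shortfall = p − p × r = p × (1 − r), above zero whenever r < 1 and p > 0
- relative shortfall = 1 − r, free of both N and p

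**Check with counts.** Take N = 420, the planned rollover figure, which SAP 3.5 says will not be reached. Let half be scored: s = 210. Let half of those have dysfunction: d = 105. Then d/s = 105/210 = 50.0% and d/N = 105/420 = 25.0%.

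**Constant prevalence** (all p and r are assumptions):

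| p among scored | r = 80% | r = 50% | r = 20% |
|---|---|---|---|
| 50% | 40% | 25% | 10% |
| 30% | 24% | 15% | 6% |

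**Prevalence needed for the row to look flat.** This is p/r, with p the prevalence at full scoring.
- From 30%: 0.30/0.80 = 37.5%; 0.30/0.50 = 60%.
- From 50%: 0.50/0.80 = 62.5%; 0.50/0.50 = 100%.
- If r falls below the starting p, even 100% dysfunction among those still scored would be printed as a fall.

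**Group contrast, if completeness differs.** With p = 50% in both groups:
- 60% versus 50% scored: 0.50 × 0.60 = 30% against 0.50 × 0.50 = 25%, a spurious 5 points
- 70% versus 50% scored: 35% against 25%, a spurious 10 points

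**Why r falls at later visits.** Early-termination, unscheduled and remote assessments enter only the window in which they fall. A subject last assessed before Day 323 counts in the Week 52 denominator and cannot count in its numerator. Subjects discontinued at the early stop before that day are all in this position.

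**The case against.** The strongest reply is that no rule is broken. SAP 5.1 allows a different denominator where one is specified, and 14.6.3 specifies one. Read literally, the percentage is the proportion of treated subjects with documented dysfunction at the visit. That is correct, and the point is not an internal contradiction. But permission to override does not make the override sound, and the SAP gives no reason for treating this endpoint differently from remission or from its other by-visit safety percentages.

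Second, a careful reader has checks. The count is printed beside the percentage. SAP 13 tabulates the CSFQ-14 total by visit and prior treatment, and the number of subjects is part of every continuous summary. The non-missing rate can therefore be approximately rebuilt. Mean CSFQ-14 change at the same visits also does not shrink mechanically with missing data. These safeguards limit the harm but do not correct the printed percentage.

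Third, the size is assumed. The documents give neither prevalence nor completeness, and nothing in them ties missingness to prior treatment; all subjects receive the same open-label drug. The group contrast is therefore conditional on unequal completeness.

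Fourth, the endpoint is exploratory, the study has no hypothesis tests, and the primary endpoint is treatment-emergent adverse events. This limits the weight of the point. Finally, the proposed denominator gives prevalence in a selected group of remaining subjects and does not remove dropout bias. That also stands, and should be footnoted.

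**Conclusion.** The concern holds. Followed as written, SAP 14.6.3 counts every unscored subject as free of dysfunction, and the printed percentage equals prevalence among scored subjects times the share scored. The direction and the relative size (the missing share) are exact and need no assumption beyond some scores being missing and some scored subjects having dysfunction. The absolute sizes are illustrations. It should be fixed before the tables are produced, but it affects one exploratory safety table and does not touch the primary endpoint.

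A smaller, separate point is missing detail. Protocol 9.5.2 promises shift tables for this endpoint. The SAP text specifies none: 5.1 speaks only of two Baselines as reference points, and Section 19 records no changes. They may be in the separate table specifications mentioned in SAP 1, so this is a query rather than a demonstrated omission.

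**What to change.** In SAP 14.6.3, make the denominator the number of subjects in the Safety Analysis Set, within the prior-treatment group, who have a non-missing CSFQ-14 total at that visit. Print that number for each visit and group. Add a footnote that the percentage describes scored subjects only and does not correct for dropout related to sexual function.

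In the same edit, specify the shift table from Protocol 9.5.2: dysfunction yes or no at Baseline against each visit, with subjects having both values as the denominator. Otherwise, point to where it is specified or record its omission in Section 19.

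The cost is one sentence of SAP text, one displayed count with a footnote, and one table specification. No new data are required.
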